Effectiveness and Safety of Pharmacopuncture Therapy for Chronic Low Back Pain: Study protocol

Protocol ID : JS-CT-2021-02

Clinical trials : NCT04833309

Document Date : September 30, 2021

Study Design and Setting

This two-armed, parallel, multi-center RCT will competitively recruit 100 patients in the Jaseng Hospital of Korean Medicine, Daejeon Jaseng Hospital of Korean Medicine, Bucheon Jaseng Hospital of Korean Medicine, and Haeundae Jaseng Hospital of Korean Medicine. The study protocol was approved by the Institutional Review Board (IRB) of Jaseng Hospital of Korean Medicine before participant recruitment (JASENG 2021-02-012, JASENG 2021-02-013, JASENG 2021-02-014, JASENG 2021-02-032). Additionally, the study protocol will be registered with Clinicaltrials. gov (NCT04833309) and Clinical Research Information Service (KCT0006088) and continuously updated.

Inclusion/Exclusion Criteria

Inclusion Criteria

- LBP onset \geq 6 months
- Numeric rating scale (NRS) score of LBP \geq 5
- Age 19–70 years
- Signing of the ICF to participate in the clinical trial

Exclusion Criteria

- Diagnosis of a serious disease that may cause LBP (eg, spinal metastasis of tumor, acute fracture, spinal dislocation)
- Progressive neurological defects or severe neurological symptoms
- Pain is caused by soft tissue disease rather than the spine (eg, tumor, fibromyalgia, rheumatic arthritis, gout)
- Other chronic diseases that may hinder the interpretation of treatment effects or outcomes (eg, stroke, myocardial infarction, renal disease, diabetic neuropathy, dementia, epilepsy)
- Current use of steroids, immunosuppressants, antipsychotic agents, or other drugs that may affect study outcomes
- Contraindications for pharmacopuncture, including hemorrhagic diseases, anticoagulant usage, severe diabetes mellitus with risk of infection
- Use of drugs that may affect pain, including non-steroidal anti-inflammatory drugs, or pharmacopuncture therapy within the previous week
- Pregnant or breastfeeding women, as well as women planning to conceive
- Lumbar surgery in the previous three months
- Less than one month since participating in another clinical trial or planning to participate in another clinical trial during the study period or follow-up period within 6 months upon enrolment
- Declining to sign a consent form to participate

- Other disqualifications as determined by the investigators

Interventions

Experimental Group: Pharmacopuncture Therapy

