The intensity of radiating leg pain in the past week will be assessed using the NRS. Patients will be asked to choose a number from 0–10 that best represents their current discomfort level (0 for no pain, 10 for the worst imaginable pain).

Visual analog scale (VAS) score of low back pain and radiating leg pain

The VAS represents the patient's pain level, where one end of a 100-mm line refers to no pain while the other end indicates the worst imaginable pain. Patients are instructed to indicate their intensity of LBP and radiating leg pain within the previous week by marking a point on the line.

Oswestry disability index (ODI)

The participants' functional status will be assessed using the ODI, which is a 10-item tool developed to assess LBP-caused disability. Each item is divided into six steps; further, it is rated on a scale from 0–5. A higher score indicates a more severe disability. We will use the Korean version of the ODI questionnaire, which has been shown to be reliable and valid.

Korean version of the Roland–Morris disability questionnaire (RMDQ)

The RMDQ is among the most widely used tools for evaluating the functional state of patients with LBP. It comprises 24 items, with the patient marking the specific activities limited by their LBP. A positive response scores 1 point, and the questionnaire is scored from 0 (minimal disability) to 24 (severe disability). We will use the questionnaire of the Korean-adapted version, which has been shown to be reliable and valid.

Patient Global Impression of Change (PGIC)

The PGIC is a self-reported tool for patients' improvement levels: 1, very much improved; 2, much improved; 3, minimally improved; 4, no change; 5, minimally worse; 6, much worse; or 7, very much worse. A consistent relationship between the change in NRS and the PGIC was demonstrated regardless of study, disease type, age, sex, study result, or treatment group.

Short Form-12 Health Survey (SF-12) version 2

The SF-12 is a questionnaire for evaluating health-related quality of life. It comprises 12 items in 8 domains: physical functioning, role-physical, bodily pain, general health, vitality, social functioning, role-emotional, and mental health. It usually takes less than five minutes to complete the questionnaire, with a higher score indicating a better health-related quality of life. We will use the Korean version SF-12, which has been shown to be reliable and valid.

5-level EuroQol-5 dimension (EQ-5D-5L)

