We will perform both intention-to-treat (ITT) and per-protocol (PP) analyses, with ITT as the primary analysis. For the PP analysis, we will include participants who complete at least seven treatment sessions over 5 weeks. Missing data will be handled by multiple imputation (MI) for analysis of covariance (ANCOVA) and comparison of area under the curve (AUC), as well as

the mixed model for repeated measures for the linear mixed model. For survival analysis, outcomes after the missing time point will be censored. For sensitivity analysis, the last observation carried forward (LOCF) will be used for missing data imputation; further, the normality of distribution will be tested. Nonparametric data will be analyzed using the Wilcoxon-rank sum test. Sociodemographic characteristics and treatment expectancy of the participants will be assessed according to the group. Continuous variables will be presented as mean (SD) or median (quartile), with between-group differences being analyzed using Student's t-test or Wilcoxon-rank sum test, depending on their distribution. Categorical variables will be presented as frequency (%) and analyzed with the chi-square test or Fisher's exact test.

The study endpoints are the differences in the extent of changes in continuous outcomes (NRS, VAS, NDI, NPQ, EQ- 5D-5L, SF-12) at each time point from the baseline. As the primary analysis, we will use a linear mixed model with the covariant factors significantly different from the baseline as covariates and the group as the fixed factor. Next, ANCOVA will be performed on sets processed by MI and LOCF.

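### Leg-pain NRS and VAS changes are averaged over all randomised patients, some of whom may enter with no leg pain, and baseline leg pain is not routinely adjusted for

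*Combined protocol and SAP*

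**What the plan says.** All places are in the combined protocol and SAP.

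- **Inclusion Criteria.** The only pain-intensity threshold is on "Numeric rating scale (NRS) score of LBP", which must be at least 5. No criterion concerns leg pain.
- **Secondary outcomes.** "The intensity of radiating leg pain in the past week will be assessed using the NRS", on a 0–10 scale where 0 is no pain. A 100-mm scale is listed as "Visual analog scale (VAS) score of low back pain and radiating leg pain". Neither outcome is limited to patients who have leg pain.
- **Statistical Methods, analysis sets.** "We will perform both intention-to-treat (ITT) and per-protocol (PP) analyses, with ITT as the primary analysis". The one restriction is on attendance: "For the PP analysis, we will include participants who complete at least seven treatment sessions over 5 weeks".
- **Statistical Methods, models.** "The study endpoints are the differences in the extent of changes in continuous outcomes (NRS, VAS, NDI, NPQ, EQ- 5D-5L, SF-12) at each time point". The mixed model takes as covariates the factors found to differ at baseline. ANCOVA follows on the imputed sets, with no covariates listed. AUC is calculated for each outcome and compared by Student's t-test.

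The endpoint list does not name leg pain. That it is covered follows from the secondary-outcome list and from the AUC comparison being applied to every outcome.

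**The concern.** A patient with back pain only starts at 0 on both leg-pain scales. That patient can get worse but cannot improve. The all-ITT mean change therefore combines patients who can benefit with patients who cannot, in a proportion that depends on who enrols. Two trials with the same effect on existing leg pain would report different leg-pain differences if their shares at 0 differed, and a reader could take a small difference to mean that radiating pain is not relieved.

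Patients at 0 also widen the spread of baseline scores, and change depends strongly on where a patient starts. Leaving baseline leg pain out of the model then costs precision. Under the plan it is included only after a chance imbalance, and never in the AUC comparison.

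**Working it through.** **1. The plan's own figure.** Sample Size Calculation gives, for low back pain, a difference of 1.37, SD 1.94, baseline–endpoint correlation 0.53, 90% power and a total of 64.

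- SD after baseline adjustment: 1.94 × √(1 − 0.53²) = 1.645.
- Normal approximation, two-sided 5%: 2 × (1.960 + 1.282)² × 1.645² / 1.37² = 30.3, so 31 per arm, 62 in total.
- With the noncentral t distribution: 32 per arm, 64 in total, which reproduces the plan.
- Withdrawal: 64 / 0.70 = 91.4, so 92, which the plan raises to 100.

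This figure concerns low back pain and the present point does not touch it. It does show that the sample size already counts on baseline adjustment.

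**2. Dilution.** Let q be the share at 0 on the leg-pain scale, E the effect in patients with leg pain, and E₀ the effect in patients at 0.

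All-ITT difference = (1 − q) × E + q × E₀

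If patients at 0 stay there, or worsen equally in both arms, E₀ = 0. Taking E = 1.37 from the low-back-pain pilot as an assumption:

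- q = 20%: 0.80 × 1.37 = 1.10
- q = 30%: 0.70 × 1.37 = 0.96
- q = 50%: 0.50 × 1.37 = 0.69

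**3. Allowing for the floor and whole-number scores.** Simulation with 4000 replicates and 35 per arm (50 less 30% withdrawal).

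- From the low-back-pain pilot: true difference 1.37, correlation 0.53.
- Assumed, not in the documents: leg-pain baseline mean 5 and SD 2, control improvement 1.0, and 10% of patients at 0 rising to 1–3 in both arms.

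| q | Adjusted difference, all ITT | Power, unadjusted change: all / subset | Power, ANCOVA: all / subset |
|---|---|---|---|
| 0 | 1.30 | – | – |
| 20% | 1.04 | 62% / 70% | 79% / 80% |
| 30% | 0.91 | 51% / 63% | 72% / 75% |
| 50% | 0.64 | 34% / 49% | 54% / 60% |

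The subset is patients with baseline leg pain above 0, where the adjusted difference stays at 1.29–1.30. The ratios to 1.30 are 0.80, 0.70 and 0.49, close to 1 − q. Simulation error on a power near 50% is about √(0.5 × 0.5 / 4000) = 0.8 points, so gaps of a point or so mean nothing.

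**4. Source of the power gain.** At q = 30%, adjusting the all-ITT analysis adds 72 − 51 = 21 points. Restricting to the subset then adds 75 − 72 = 3. With 50 per arm, ANCOVA power for all ITT against the subset is 92% against 93% at q = 20%, and 86% against 89% at q = 30%.

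**5. What the subset cannot see.** Suppose q = 30% and, among patients at 0, 10% on control but 40% on treatment rise to 1–3 (average rise 2). Then E₀ = −(0.40 − 0.10) × 2 = −0.60, and the all-ITT difference is 0.70 × 1.30 − 0.30 × 0.60 = 0.73. The simulation gives the same. The subset still shows 1.30.

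**The case against.** The strongest reply is that this is a choice of what to estimate, not an error. The all-ITT mean answers what happens to leg pain in the enrolled population, and nowhere does the plan say that the outcome is meant for patients with leg pain only. That stands.

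A reader might go further and infer that the all-ITT estimate is invalid, or that the subset should replace it as the main leg-pain analysis. The documents do not support either step. Patients at 0 are not a structural zero, because new radiating pain can appear, and step 5 shows that the subset would miss a difference between arms in new leg pain.

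Other objections also stand in part:

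- The share at 0 is undocumented. If it is near zero, little changes.
- The effect and correlation are low-back-pain figures borrowed for leg pain, and the baseline mean and SD are assumed.
- ANCOVA is already planned, and with baseline adjustment the subset gains little power. But the plan does not say that baseline leg pain is an ANCOVA covariate, and the mixed model and AUC do not include it by default.
- The simulation compares change scores by t-test and ANCOVA. It does not run the mixed model or the AUC comparison, so its unadjusted figures only indicate what those analyses would lose.
- A cut-off just above 0 is a convention. A patient at 1 is almost as limited by the floor, and applying the rule scale by scale can give slightly different NRS and VAS subsets.
- Randomisation is not stratified by leg pain, so balance within the subset holds only on average.

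**Conclusion.** The point holds as a gap in specification for two secondary outcomes. On the natural reading of Statistical Methods, leg-pain NRS and VAS are analysed in all ITT patients, with no routine adjustment for baseline leg pain and no analysis that shows the effect where leg pain was present. The all-ITT difference is valid for the enrolled population but is smaller than the effect in patients with leg pain by roughly the share at 0, provided patients at 0 fare alike in both arms.

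Under the borrowed and assumed inputs above, about 1.3 becomes about 1.05 at 20%, 0.9 at 30% and 0.65 at 50%. These are illustrations and not predictions, because the share is unknown.

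It would be wrong to infer that the trial's main conclusion is at risk. The entry threshold keeps every patient off the floor of the primary low-back-pain NRS, and neither the sample size nor the non-inferiority test uses leg pain.

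**What to change.** In Statistical Methods:

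1. State that leg-pain NRS and leg-pain VAS are analysed, and always adjust for the baseline score on the same scale in the mixed model, in ANCOVA and in the AUC comparison. For AUC this means replacing the t-test with a baseline-adjusted comparison.
2. Keep the all-ITT leg-pain analysis, which also captures new leg pain.
3. Add a pre-specified analysis in ITT participants whose baseline leg pain is above 0 on the scale concerned. The subset is fixed by a score taken before treatment, so the comparison remains randomised. Naming it in advance avoids the appearance of a choice made after seeing the data.
4. Report the number of participants at 0 per arm.

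The cost is a few sentences, one filter and one more secondary analysis, with no new data. The downside is that the added analysis uses a smaller group, not stratified at randomisation, and does not capture new leg pain, so it should be read beside the all-ITT result.

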A pilot study was conducted to compare the effectiveness of pharmacopuncture and physiotherapy in patients with chronic LBP. The between-group difference in the mean reduction of the NRS score for LBP was 1.37 ± 1.94 at the primary endpoint, which is immediately after the 5-week treatment; further, Cohen's d was calculated as 0.71. The correlation between the baseline and endpoint was 0.53. Given a significance of 95% and power of 90%, the sample size was calculated to be 64. Considering a 30% withdrawal rate and the recruitment of participants from four facilities, we aim to recruit 100 patients.

Recruitment

Participants will be recruited using a press release, advertisement posters at the clinical trial facility, and online recruitment sites.

Randomization and Allocation Concealment

A statistician will randomize patients into two groups at the same ratio (50 persons for each) using a randomization table on R studio 1.1.463 (© 2009-2018 R Studio, Inc.). The random sequence will be performed using block randomization; further, the size of each block will be randomly set to 2 or 4. The randomization results will be placed in a sealed opaque envelope and stored in a double-locked cabinet by a third person not involved in the study. The coordinator at each study facility will open the envelope for group allocation. Only participants who provide an ICF will be randomly assigned. The randomization number assigned to each participant will be recorded in the electronic medical record.

Blinding

Since blinding the practitioner administering the treatment and the participants is impossible due to the nature of the intervention, only the outcome assessors will be blinded. Outcome-assessors not involved in the procedure and blinded from the group allocation will perform the assessment before the procedure in an isolated space.

Data Collection and Management

We will use an e-CRF using the Internet-based Clinical Research and Trial management system (iCReaT). The principal investigator will train the outcome assessors and investigators of each facility on the standard operating procedure (SOP) as a reference for the study procedures, including writing a CRF and entering data. A query will be issued for a range check of data values. Data entered into the e-CRF will be cleaned and locked to prevent access by investigators other than the one in charge of data management.

Statistical Methods

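### The primary mixed model picks its covariates by a baseline significance test, so the covariate set is not fixed in advance and adjustment for baseline NRS is not assured (a low-cost improvement).

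*Combined protocol and SAP*

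**What the plan says.** All of the analysis text is in the Statistical Methods section of the combined protocol and SAP.

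- Primary model: a "linear mixed model with the covariant factors significantly different from the baseline as covariates and the group as the fixed factor". No covariate is named.
- Endpoint form: "The study endpoints are the differences in the extent of changes in continuous outcomes", taken from baseline at each time point.
- Supporting analysis: "Next, ANCOVA will be performed on sets processed by MI and LOCF". The ANCOVA covariates are not named either.
- Baseline comparisons: "Sociodemographic characteristics and treatment expectancy of the participants will be assessed according to the group". Baseline NRS is not mentioned there.

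The Sample Size Calculation section gives "The between-group difference in the mean reduction of the NRS score for LBP was 1.37 ± 1.94 at the primary endpoint", then "The correlation between the baseline and endpoint was 0.53", and concludes "Given a significance of 95% and power of 90%, the sample size was calculated to be 64". It names no formula. The Inclusion Criteria require a "Numeric rating scale (NRS) score of LBP" of at least 5, so a baseline NRS value is collected on everyone.

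**The concern.** A baseline test of group against group asks whether randomisation produced an unusual imbalance. It does not ask whether a variable predicts the outcome, and prediction is what justifies adjustment. Choosing covariates this way has three consequences.

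1. The covariate set of the primary model cannot be written down before the data are seen. Patients and practitioners are unblinded here, so a fixed set is a cheap safeguard.
2. Baseline NRS, the obvious prognostic variable, will usually be left out. A change score only partly replaces it, because it forces the slope on baseline to be 1.
3. When baseline NRS is imbalanced but not significantly so, the unadjusted change score carries a bias conditional on that imbalance. If the same estimate and confidence interval serve the fallback non-inferiority test, with its margin of -1 NRS point, the covariate choice reaches that conclusion too.

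**Working it through.** **Inputs.** From Sample Size Calculation: difference 1.37, SD 1.94, d stated as 0.71 (1.37/1.94 = 0.706), baseline-endpoint correlation r = 0.53, power 90%. Alpha is 0.05, taken as two-sided. The document does not say whether 1.94 is the SD of the change or of the endpoint, and gives no baseline SD. Both readings of 1.94 and a range of baseline SDs are therefore used.

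**Step 1: the plan's 64.** Per arm, n = 2(1.960 + 1.282)² × f / d², where f is the variance factor. Totals are shown as normal approximation / noncentral t.

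| Use of r | f | d = 1.37/1.94 | d = 0.71 |
|---|---|---|---|
| none | 1 | 86 / 88 | 84 / 86 |
| 1 - r² | 0.719 | 62 / 64 | 60 / 62 |
| (1 + r)/2 | 0.765 | 66 / 68 | 64 / 66 |
| 2(1 - r) | 0.94 | 80 / 82 | 80 / 82 |

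The figure 64 appears twice. The factor 1 - r² is baseline adjustment with 1.94 as the endpoint SD. The factor (1 + r)/2 equals (1 - r²)/[2(1 - r)], which is baseline adjustment with 1.94 as the change SD and equal SDs at both times. It can also mean averaging two measurements with no baseline covariate. That 64 assumes baseline adjustment is thus a reasonable inference, held with moderate confidence, and the concern does not depend on it.

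**Step 2: how often the rule admits baseline NRS.** Tested at 0.05 under randomisation, about 5% of the time (4.8% to 5.2% in simulation).

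**Step 3: power at 64 evaluable, difference 1.37.** With baseline SD sx and endpoint SD sy:

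- Change SD = √(sx² + sy² - 2·r·sx·sy), analysed by t test on 62 df.
- Adjusted residual SD = sy√(1 - r²), analysed by ANCOVA on 61 df and averaged over chance imbalance.
- If 1.94 is the change SD, sy is solved from the first formula.

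Example at sx = 1.7:

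- 1.94 as endpoint SD: change SD √(2.890 + 3.764 - 3.496) = 1.777; residual SD 1.94 × 0.848 = 1.645.
- 1.94 as change SD: sy = 2.199; residual SD 1.865.

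Power (%), unadjusted change / baseline-adjusted:

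| Baseline SD | 1.94 = endpoint SD | 1.94 = change SD |
|---|---|---|
| 1.0 | 90.6 / 90.2 | 79.4 / 79.2 |
| 1.2 | 90.3 / 90.2 | 79.4 / 78.7 |
| 1.5 | 88.3 / 90.2 | 79.4 / 79.7 |
| 1.7 | 85.9 / 90.2 | 79.4 / 81.8 |
| 1.94 | 81.8 / 90.2 | 79.4 / 86.6 |
| 2.0 | 80.6 / 90.2 | 79.4 / 88.3 |

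At SD 1.0 to 1.2 adjustment costs 0.2 to 0.7 points. With 70 evaluable (100 less 30%) the loss from not adjusting is about 0 to 2 points at SD 1.5, 2 to 4 at 1.7 and 7 to 9 at 1.94 to 2.0. With 100 evaluable it is at most about 4.

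**Step 4: precision.** The approximate 95% half-width at 64 is t × SD × √(2/32). At sx = 1.7 it falls from 2.00 × 1.94 × 0.25 = 0.97 to 2.00 × 1.865 × 0.25 = 0.93 (1.94 as change SD), or from 0.89 to 0.82 (1.94 as endpoint SD).

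**Step 5: conditional bias.** Given an observed baseline difference D, the unadjusted change score is biased by (b - 1)D, with b = r·sy/sx. At sx = 1.7, b is 0.605 (endpoint SD) or 0.686 (change SD). With the observed SD at 1.7, D is 0.71 at p = 0.10 and 0.85 at p = 0.05. The size of the bias runs from 0.314 × 0.71 = 0.22 to 0.395 × 0.85 = 0.34 NRS points. Averaged over p from 0.05 to 0.10, which is about 5% of trials, it is within about 0.1 at SD 1.0 to 1.2, 0.15 to 0.21 at 1.5, 0.24 to 0.30 at 1.7, and 0.37 to 0.43 at 1.94 to 2.0.

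**Step 6: the rule itself.** This was simulated with 40,000 bivariate normal trials per setting: ANCOVA if baseline p < 0.05, otherwise unadjusted change. Type I error was 4.2% to 5.1%. Power lost at 64 against always adjusting was -0.7 to -0.2 points at SD 1.0 to 1.2, 0.4 to 1.6 at 1.5, 2.3 to 4.1 at 1.7, and 6.3 to 8.6 at 1.94 to 2.0. At 100 it was at most 3.3.

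**The case against.** The case for leaving the rule alone has substance.

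- **The large losses need a baseline SD that is hard to reach.** Entry at NRS 5 or more truncates the scale. Even an equal spread over the integers 5 to 10 has SD 1.71. This stands: 7 to 10 points is an upper end, and at low SD the adjustment gains nothing.
- **Baseline is already partly handled.** The endpoint is change from baseline and an ANCOVA follows. This stands in part. The change score fixes the slope at 1, and the ANCOVA is secondary with unstated covariates.
- **A repeated-measures model could carry baseline NRS as a response,** recovering most of the precision without a covariate. The plan neither states nor excludes this, and it fits poorly with an endpoint defined as change. The power figures apply to a model without that feature.
- **The simulation covers one candidate covariate at one time point,** whereas the rule covers an unlisted set. This stands as a limit on the type I error result.
- **The fix leaves time, group-by-time, site and covariance terms open.** This is also true, so what becomes fixed in advance is the covariate set, not the whole model.

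None of this supports choosing covariates by a baseline test.

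**Conclusion.** The concern holds, as a minor point. With high confidence, the plan lets a significance test on trial data choose the primary model's covariates and nowhere fixes baseline NRS as one of them. The size is less certain, because it depends on an unstated baseline SD, on what 1.94 measures, and on a single-time-point normal approximation to a repeated-measures design with partial completers. At baseline SDs up to 1.7 the power cost at 64 evaluable is between nothing and about 5 points, and smaller with more patients. The conditional bias averages out over randomisations, and no inflation of type I error was found. If 1.94 is the change SD, adjusted power at 64 stays below 90% at every baseline SD examined (at most 88.3%), so the fix should not be presented as securing the planned power.

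**What to change.** Replace the covariate rule in Statistical Methods with:

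> The primary linear mixed model and the ANCOVAs on the MI and LOCF sets adjust for the baseline value of the outcome analysed (baseline NRS of LBP for the primary outcome), fixed in advance; no covariate is selected by a baseline significance test.

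Do not add a statement that 64 assumes this analysis unless the sponsor confirms the formula used and whether 1.94 is the SD of the change or of the endpoint.

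The cost is a wording change and one degree of freedom. No extra patients or measurements are needed. If the baseline SD proves to be 1.0 to 1.2, the adjustment costs up to 0.7 points of power at 64 evaluable.

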To compare the total difference in each outcome within a certain period (treatment period and total study period), the AUC will be calculated for each time point after randomization and compared using Student's t-test. Further, the proportion of patients whose NRS and VAS scores dropped by > 50% from the baseline values will be compared at each time point. The time from randomization to lumbar recovery, which was defined as > 50% reduction in the pain indices, will be compared using Kaplan-Meier survival analysis. Further, the curves will be compared using the Log rank test. Additionally, hazard ratios will be compared using the Cox proportional hazard model. The significance level will be set at 0.05 for all analyses. All statistical analyses will be performed using the SAS 9.4 (© SAS Institute, Inc., Cary, NC, USA) or R studio 1.1.463 (© 2009-2018 RStudio, Inc.) software. Statistical significance will be set at $p < 0.05$.

In case the superiority test fails, a non-inferiority test will be performed. The non-inferiority margin will be set to -1 (NRS), which represents half of the minimal clinically important difference. Pharmacopuncture will be considered non-inferior to physiotherapy if the lower bound of the 95% confidence interval (CI) of the between-group difference of the NRS score reduction does not exceed the non-inferiority margin.

Data Monitoring

The monitoring staff will supervise the clinical trial process, as well as periodically review and confirm whether the study is performed and recorded according to the protocol, SOP, clinical trial management standards, and applicable regulations. The clinical trial will be monitored by the monitoring staff of each clinical trial facility and the sponsor institution using periodic visits and phone calls. At the monitoring visits, the monitoring staff will check the original participant records and data storage (study files). Further, they will inspect the clinical trial procedure and discuss any problems with the investigators.

In case of unexpected or unacceptable risks to participants or occurrence of serious adverse events related to pharmacopuncture or physiotherapy in $\geq 25\%$ of the participants, the clinical trial may be paused. The analysis will be only accessed by the statistician and principal investigator; additionally, the final decision to terminate the study will be made by the principal

investigator

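### The AUC comparison is an unadjusted t-test although baseline is available for the listed continuous outcomes: valid, but less precise than a baseline-adjusted analysis of the same data

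*Combined protocol and SAP*

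**What the plan says.** Four statements bear on this point.

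- **The test.** Under Statistical Methods, an AUC is formed from the time points after randomisation and "compared using Student's t-test". It is to be done for each outcome over two windows, the treatment period and the total study period. No covariate is mentioned.
- **Missing values.** The same section says "Missing data will be handled by multiple imputation (MI) for analysis of covariance (ANCOVA) and comparison of area under the curve (AUC"). Imputation completes the data; it does not adjust the comparison of arms for baseline.
- **Baseline.** The endpoints are defined as changes "at each time point from the baseline", so a baseline value exists for the listed continuous outcomes. ANCOVA is planned for those endpoints on the imputed sets, although its covariates are not named.
- **Correlation.** Sample Size Calculation reports: "The correlation between the baseline and endpoint was 0.53". This is the only baseline correlation in the document.

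The document gives no visit schedule. It does not say whether the AUC is built from raw scores or changes, or whether the baseline point is part of the area.

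**The concern.** A patient's average pain over several weeks is usually related to the pain at entry. A two-sample t-test on such an average leaves that between-patient variation in the error term, although the baseline value is on file. Two things follow. The standard error of the AUC difference is larger than it need be, and any chance difference between arms at entry stays in the observed estimate. The sample size appears to count on the baseline correlation, so a t-test on a summary of the same outcome does not use information on which the design relies.

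**Working it through.** **1. The plan's sample size.** Inputs from Sample Size Calculation: "The between-group difference in the mean reduction of the NRS score for LBP was 1.37 ± 1.94 at the primary endpoint"; "Cohen's d was calculated as 0.71"; correlation 0.53; power 90%. Alpha is 0.05; two-sided is assumed because sidedness is not stated.

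- d = 1.37 / 1.94 = 0.706.
- ANCOVA variance factor = 1 − 0.53² = 1 − 0.2809 = 0.7191.
- With the factor (noncentral t): 32 per arm, **64 in total**, as stated.
- Without it: 44 per arm, 88 in total.
- One-sided with the factor: 50 to 52 in total.

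So 64 matches only with baseline adjustment. This is inferred from the match; the plan does not name the formula. With d rounded to 0.71 the adjusted total is 62. If 1.94 is already the SD of change scores, the factor would be (1 + 0.53)/2 = 0.765 under equal variances, and the total would be 68.

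**2. One post-baseline raw score.** The share of variance removable by adjustment is the squared correlation between baseline and the quantity compared.

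- 0.53² = 0.281, so 28%.
- Ratio of standard errors, unadjusted to adjusted: 1/√0.7191 = 1.18.
- Ratio of patients needed: 1/0.7191 = 1.39.

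**3. AUC over several visits.** Assumptions not in the documents: five weekly post-baseline visits, equal variances, and a correlation that is either the same for every pair (compound symmetric, 0.53) or decays serially (AR(1), 0.53 between baseline and week 5).

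Compound symmetric case by hand:

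- Mean of five raw scores: variance (1 + 4 × 0.53)/5 = 0.624; covariance with baseline 0.53. Share = 0.2809/0.624 = 0.45.
- Trapezoid including baseline: covariance (0.5 + 4.5 × 0.53)/5 = 0.577; variance (4.5 × 0.47 + 25 × 0.53)/25 = 0.615. Share = 0.577²/0.615 = 0.54.
- Mean of five changes: covariance 0.53 − 1 = −0.47; variance 0.624 + 1 − 1.06 = 0.564. Share = 0.2209/0.564 = 0.39.

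| Removable variance, equal variances | Compound symmetric | AR(1) |
|---|---|---|
| Raw AUC, post-baseline visits only | 44–45% | 56–58% |
| Raw AUC, trapezoid including baseline | 54% | 67% |
| AUC of change scores | 39% | 20–21% |

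**4. Narrower baseline spread.** Entry requires NRS of at least 5, so baseline runs from 5 to 10. Equal variances with a change SD of 1.94 imply a score SD of 1.94/√(2 × 0.47) = 2.0, but even a uniform spread over the integers 5 to 10 has an SD of only 1.71. Take baseline SD from 1.0 to 1.7, and find the later SD s from 1.94² = b² + s² − 2 × 0.53 × b × s.

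- b = 1.2 gives s = 2.29. The ratio is 0.52, close to 0.53, so the change is almost uncorrelated with baseline: 0% (compound symmetric), 7 to 10% (AR(1)).
- b = 1.7 gives s = 2.20. Compound symmetric: covariance 0.53 × 3.74 − 2.89 = −0.908; variance 0.624 × 4.84 + 2.89 − 1.06 × 3.74 = 1.946. Share = 0.908²/(1.946 × 2.89) = 15%.

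Over 1.0 to 1.7 and both patterns, a change-score AUC gains 0 to about 18%. A raw-score AUC still gains about 44 to 66%.

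**5. Chance imbalance.** With 50 per arm, the 95% range of the baseline difference is ±1.96 × √(2/50) = ±0.39 SD. At correlation 0.53, about 0.53 × 0.39 = ±0.21 SD of this passes into an unadjusted comparison at a single visit. The planned effect is 0.71 SD.

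**The case against.** The strongest reply is that nothing here is invalid. Under randomisation the t-test is unbiased, holds its type I error, and already carries chance imbalance in its standard error. That stands. A reader might infer that imbalance at entry is mistaken for a treatment effect in a way that biases the result; it is not, on average. What remains is avoidable error in the trial actually run.

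A second reply is that the size is uncertain. That also stands. A reader might infer that half or more of the precision is always lost. The documents do not support this: their only correlation gives 28% for one raw score, and half needs a correlation of at least √0.5 = 0.71 with the AUC. Several raw-score visits can produce that, but the endpoints are defined as changes, and a change-score AUC already removes much or nearly all of the dependence on baseline. Power figures for the AUC would also need an assumed schedule, effect course and evaluable number, so none is claimed here.

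Third, a reader might infer that this is the only unadjusted continuous comparison, or that every outcome has a baseline value. Neither holds. A Wilcoxon rank-sum test is planned for nonparametric data, the ANCOVA covariates are unnamed, and the mixed model includes only factors found to differ significantly. PGIC is itself a rating of change.

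Finally, the AUC is supplementary: the primary analysis is the linear mixed model, and neither the sample size nor the non-inferiority fallback uses the AUC. This limits the consequence but is no reason to keep the less efficient test.

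**Conclusion.** The point holds as a matter of precision, not validity. The stated AUC test is unadjusted, and nothing elsewhere in the plan adjusts it. The removable variance is 28% for a single post-baseline raw score at the stated correlation. With five weekly visits and the two correlation patterns above, all assumed, it is 44 to 67% for a raw-score AUC and about 0 to 39% for a change-score AUC. The low end of the latter applies if the entry criterion narrows the baseline SD. All figures take the NRS correlation of 0.53 as given; the other outcomes may differ. The primary result is unaffected.

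**What to change.** Replace the t-test for the AUC by a prespecified ANCOVA: AUC on group, with the baseline value of the same outcome as covariate and, optionally, site, fitted in each imputed data set and pooled. Outcomes without a baseline value, such as PGIC, are excepted. The t-test can stay as a descriptive check.

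In the same sentence, state the visits that enter the AUC, whether raw scores or changes are used, and whether the baseline point is included. Once baseline is a covariate, raw and change versions with the same visit weights give the same treatment estimate, because they differ only by a multiple of baseline. The adjusted result therefore no longer depends on that choice.

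The cost is one or two sentences and one model line: no new data, one degree of freedom for baseline, and three more if the four sites are included. Fixing the covariate now also rules out a choice made after the results are seen.
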